Health literacy will be assessed using the Knowledge About Schizophrenia Test (KAST). An assessment for attitudes toward treatment will be developed specifically for this study, with guidance from the Drug Attitude Inventory (DAI) and the Attitudes towards Neuroleptic Treatment (ANT), which was found to be useful in the quantitative assessment of attitudes before and after initiation of neuroleptic medication [29]. The National Alliance on Mental Illness (NAMI) will be used to guide the development of inpatient educational resources.

We hypothesize that health literacy scores and attitude towards treatment will improve following educational intervention. A possible limitation of this study is the effect of concomitant intellectual disability (ID) on an individual's ability to comprehend the provided educational resources. Therefore, we plan to exclude patients with a documented history of intellectual disability and patients suspected to have intellectual disability based on clinical interactions. We also plan to follow up with participants monthly, where we will utilize tools such as the Medication Adherence Rating Scale (MARS) to provide further insight into adherence to treatment plans [30,31].

We believe the information provided from this study can be of great significance in strengthening the patient-provider relationship, building a community, and dissolving the stigma around mental health, while simultaneously empowering and encouraging patients to get more involved in their care. Due to the contribution of mental health literacy on healthcare outcomes, we believe such an intervention can prove to be unequivocal in decreasing the health equity gap in mental health disorders and beyond. At the minimum, it will provide necessary insight into the needs of this underserved and highly vulnerable population and guidance on navigating their treatment.

Study Aims/Objectives

- a. Assess health literacy level as it relates to schizophrenia before and after provision of educational resources.
- b. Assess the attitude toward treatment of each patient before and after provision of educational resources.
- c. Create and provide inpatient educational resources in the form of audiovisual and textual infographics developed by the Louisiana State University Health Sciences Center- New Orleans, Department of Psychiatry.

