- d. Collect and analyze patient- centered data, including age, gender, ethnicities, and highest level of education, to identify any trends in healthcare literacy as measured by the KAST across these demographics.

Primary endpoints: Post- intervention KAST and ATT scores

Secondary endpoints: MARS scores, KAST and ATT scores in relation to demographics (age,

gender, ethnicity, highest level of education) collected

Study Design

Inclusion Criteria

- i. Patients admitted to the University Medical Center-New Orleans (UMCNO) inpatient behavioral health unit ages 18 and older with a new or previous diagnosis of schizophrenia spectrum disorder outside of substance use disorders
- ii. Patients must be proficient in English.
- iii. Patients must have a government issued social security number (required for reimbursement through the university).

Exclusion Criteria

- i. Patients at UMCNO that are ages 17 or younger
- ii. Patients with SSD and concomitant intellectual disability, as evidenced by prior documented history on chart review or patients suspected to have intellectual disability or impairment based on clinical interactions
- iii. Patients with concomitant substance use and documentation of psychosis being resolved after a period of washout and without the use of psychotropic medications
- iv. Patients unable to complete health literacy assessments, attitude towards treatment assessments, and IQ testing due to severity of symptoms during hospitalization
- v. Patients that are not proficient in English
- vi. Patients that do not have a government issued social security number

Study Assessments and Outcome Questionnaires

The Knowledge about Schizophrenia Test (KAST):

The KAST [24] is an 18-item multiple-choice test designed to measure knowledge about schizophrenia. The questions focus on knowledge of development, symptoms, treatments, and supporting information about schizophrenia.

Attitudes towards Neuroleptic Treatment (ANT):

The ANT [29] is a 12-item questionnaire assessing attitudes using a visual analogue scale form in which participants note their opinions on a scale of 0-100 for each statement.

Drug Attitude Inventory (DAI):

The Drug Attitude Inventory is a 30-item questionnaire assessing attitudes toward medication using a true-false format.

Medication Adherence Rating Scale (MARS):

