Abnormal Pregnancy Outcomes (e.g. spontaneous abortion, fetal death, stillbirth, congenital anomaly, ectopic pregnancy)	Within 15 calendar days of becoming aware of the event(s)	By a secure means, as agreed by the Parties, on a Serious Adverse Event Form.
Lack of Effect (with or without a suspected adverse reaction), must be reported as an SAE.	Within 15 calendar days of becoming aware of the event(s).	By a secure means, as agreed by the Parties, on a Serious Adverse Event Form.
Product Quality Complaints	Within 3 business days of becoming aware of the event(s)	By a secure means, as agreed by the Parties.
Non-Serious Adverse Event* (*Not meeting other listed 3 business day reporting criteria e.g. AESI)	Annually and in final study report.	Recorded in CRF and reported annually and in final study report.
Follow-up information	Transmitted within the same timeframes as above i.e. if initial report was required to be submitted within 15 calendar days, follow-up information shall be submitted within the same timeframe.	Transmitted via same method as above i.e. if initial method of transmission was on an SAE form, follow-up information shall be transmitted in the same manner.

Janssen SAE/Pregnancy Notifications	
TO: [contact]
 
Please note the underscores (_) in the email name this is critical to highlight as if its missing then the SAE will fail to transmit.
 
CC: Janssen SRS/SRP and Clinical Project Scientist

-------------------------------------	--

Janssen PQC:	[contact] CC: Janssen SRP/CPS
Janssen [contact]

Statistical analysis

A power analysis resulted in the two possible sample sizes as shown below:

*An a priori power analysis was performed using g*power to estimate sample size for a paired sample t-test. Using a small effect size ($d=.2$), power of 80% (alpha of .05), the desired sample size is 199.*

*An a prior power analysis was performed using g*power to estimate sample size for a paired sample t-test. Using a medium effect size ($d=.5$), power of 80% (alpha of .05), the desired sample size is 34.*

Per literature review, studies with educational interventions in patients with SSD had sample sizes ranging from 20s to several hundreds. None of the studies provided information on power analysis calculations or how sample size was obtained. Given that we will not have access to 200 patients with schizophrenia spectrum disorders at the study site within the time frame of the study, we have chosen to use the former power analysis.

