To assess changes in knowledge and attitudes, a paired samples t-test will be completed on pre-intervention and post-intervention scores for the KAST and ATT. Demographic data will be analyzed using regression analysis.

Data Collection and Storage

Each study participant will be given an arbitrary study identification number. The study ID number will be used on all data collected for the purposes of this study. All assessments and questionnaires for this study will be entered using a tablet into the REDCAP system, a secure and HIPAA compliant web-based system provided through LSUHSC- New Orleans for data collection. Permission to access the project's Research Electronic Data Capture (REDCAP) program must be approved by an investigator or study coordinator. Participants and linking study identification numbers will be kept in a database outside of the REDCAP system on the LSUHSC-NO secure network drive in a folder that can only be accessed by individuals given permission by the primary investigator and study coordinator. This information will also be protected by a password only known to the study personnel. Informed consent forms will be kept in individual participant files which will be in locked file cabinets in a locked door.

Data extracted from the medical records will also be given an arbitrary study ID. This data will be collected using the REDCAP system. To track patient data that has been retrieved, a separate database will be kept on the LSUHSC-NO network drive linking the patient's medical

requisition number with the arbitrary study ID. This database will also be protected by a password only known to study personnel.

After the data has been analyzed and the study closed, data will be destroyed in compliance with LSUHSC-NO Institutional Review Board requirements.

Citations

1. Coleman, K. J., Stewart, C., Waitzfelder, B. E., Zeber, J. E., Morales, L. S., Ahmed, A. T., Ahmedani, B. K., Beck, A., Copeland, L. A., Cummings, J. R., Hunkeler, E. M., Lindberg, N. M., Lynch, F., Lu, C. Y., Owen-Smith, A. A., Trinacty, C. M., Whitebird, R. R., & Simon, G. E. (2016). Racial-Ethnic Differences in Psychiatric Diagnoses and Treatment Across 11 Health Care Systems in the Mental Health Research Network. *Psychiatric services (Washington, D.C.)*, 67(7), 749–757. <https://doi.org/10.1176/appi.ps.201500217>

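### Two unranked primary endpoints, KAST and ATT, are each given a t-test, but the size is worked out for one test: the 5% and 80% hold per test, not for the pair

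*Protocol*

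**What the plan says.** Under Study Aims/Objectives the protocol states "Primary endpoints: Post- intervention KAST and ATT scores", with neither score ranked above the other. The hypothesis, in the Introduction, is worded jointly: "We hypothesize that health literacy scores and attitude towards treatment will improve following educational intervention".

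The Statistical analysis section says that "a paired samples t-test will be completed on pre-intervention and post-intervention scores for the KAST and ATT". It attaches no significance level, order or success rule to those tests.

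The sizing, in the same section, was done "to estimate sample size for a paired sample t-test", and two results are offered: "Using a small effect size ($d=.2$), power of 80% (alpha of .05), the desired sample size is 199" and "Using a medium effect size ($d=.5$), power of 80% (alpha of .05), the desired sample size is 34". The alpha in these two sentences is the only significance level in the document.

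**The concern.** Two primary tests are planned and one is sized. A reader will take the stated alpha and power as properties of the study's main conclusion, but that conclusion is not defined. The protocol does not say whether the study succeeds when either score improves, when both do, or whether the two scores are judged separately.

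If either score is enough and nothing is adjusted, there are two chances of a false positive. If both are needed, there are two chances of missing a true effect. With no rule fixed in advance, the reading could also be chosen after the results are known.

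**Working it through.** **Inputs.** From Statistical analysis: alpha 0.05, power 80%, d = 0.5 with N = 34, d = 0.2 with N = 199, paired t-test. From Study Aims/Objectives: two primary endpoints. Assumed, because the protocol gives neither: the same d on both endpoints, and a correlation r between the KAST and ATT changes of 0 to 0.7.

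**Step 1. Reproduce the stated sizes.** Power of a paired t-test comes from the noncentral t distribution with n − 1 degrees of freedom and noncentrality d × √n.

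- d = 0.5: two-sided 0.05 gives N = 34 (noncentrality 0.5 × √34 = 2.92, power 80.8%). One-sided 0.05 would give 27.
- d = 0.2: two-sided 0.05 gives N = 199 (noncentrality 0.2 × √199 = 2.82, power 80.2%). One-sided 0.05 would give 156.

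Both stated sizes are right for one two-sided test. The protocol does not state sidedness; it is inferred from this match.

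**Step 2. Error for the pair, each test at two-sided 0.05, no true change on either score.**

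- At least one significant result in either direction, independent tests: 1 − 0.95² = 9.75%. By simulation with n = 34: about 9.5% at r = 0.3, 9.1% at r = 0.5, and 8.3% to 8.5% across separate runs at r = 0.7.
- At least one false *improvement*: one two-sided test gives 2.5%, so two independent tests give 1 − 0.975² = 4.9%. By simulation: 4.8%, 4.7% and 4.2% at r = 0.3, 0.5 and 0.7 (differences of 0.1 to 0.2 points between runs are simulation noise).

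**Step 3. Power for both, each test at two-sided 0.05.** With independent changes this is the square of the single-test power: 0.808² = 65% at N = 34 and 0.802² = 64% at N = 199.

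| r | N = 34, d = 0.5 on each | N = 199, d = 0.2 on each |
|---|---|---|
| 0 | 65% | 64% |
| 0.3 | 67–68% | 67% |
| 0.5 | 70% | 69% |
| 0.7 | 72% | 71% |

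**Step 4. What particular rules would give.**

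| Rule | Overall two-sided error | Power at N = 34, d = 0.5 on each | N for 80% |
|---|---|---|---|
| Fixed order, each at 0.05 | at most 5% | 80.8% for the first, 65–72% for both | 34 for the first (199 if d = 0.2) |
| Bonferroni, 0.025 each, either counts | at most 5% | 71.3% per endpoint, 82–92% for at least one | 41 per endpoint (241 if d = 0.2) |
| Both required, each at 0.05 | at most 5% | 65–72% for both | 44 for both if r = 0 (260 if d = 0.2) |

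**The case against.** **Each aim stands on its own.** Knowledge and attitude are listed as separate objectives, and the power statement speaks of one test. On that reading each test has 5% error and 80.8% power at 34 pairs, as stated, and the protocol never promises an error rate for the study as a whole. This stands. A reader might infer that no reading delivers both stated figures, but that goes too far: the per-test reading does, a fixed order does for its first endpoint, and a Bonferroni rule with success on either score holds 5% with 82% to 92% power for at least one success. What is missing is a statement of which rule applies.

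**The 9.75% is not the risk of a false claim of benefit.** A reader might infer that the chance of wrongly announcing an improvement nearly doubles from 5%. It does not. The 9.75% counts significant worsening as well. The chance of a false improvement on at least one score rises from 2.5% to at most 4.9%, so it roughly doubles but does not exceed 5%.

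**Testing each score at 0.05 is not written down.** Correct. The level appears only in the sizing sentences, and its use for each test is an inference.

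**The word *and* in the hypothesis is not a decision rule.** Also correct. It does not make the endpoints co-primary, so the 65% to 72% is the power of one possible claim and not a proven shortfall.

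**A statistical analysis plan may set the order.** It may, and its absence here is no fault. But the endpoints and the sample size are fixed in this protocol. Splitting alpha at the stated size would leave 71.3% per endpoint, requiring both would leave 65% to 72%, and a fixed order would rank endpoints that the protocol leaves equal. In each case the protocol's power statement would need qualifying.

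**The size is itself unclear.** The protocol says "we have chosen to use the former power analysis", which points to 199, while its reason (too few patients) points to 34. That is a separate matter. This point holds at either size with the d that belongs to it. If 199 were enrolled and d were 0.5 on both scores, power for both would be near 100%.

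**Conclusion.** The point holds in a limited form. The sample sizes are correctly calculated for a single two-sided paired t-test, and the stated 5% and 80% are true of each primary test taken alone. They are not true of the pair. With no adjustment, at least one false significant result occurs in about 8.5% to 9.8% of such studies with no true change (about 4.2% to 4.9% counting only false improvements), and both improvements are shown in about 65% to 72% of studies in which both exist.

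These figures rest on two-sided 0.05 for each test, the protocol's d on both scores, and a correlation of 0 to 0.7 between the changes. The weight is moderate: this is a single-group before-and-after study with no explicit commitment to control the overall error. It is still worth correcting, since as written two unadjusted primary tests rest on a size meant for one.

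**What to change.** State in the protocol that KAST is tested first at two-sided 0.05, and that ATT is tested at two-sided 0.05 only if KAST is significant. Naming KAST the single primary endpoint and ATT the key secondary would do as well. Add that the 80% power applies to KAST alone, and that power for claiming both is about 65% to 72% under the assumptions above.

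This order fits the protocol's own reasoning, in which filling gaps in knowledge is the route to better attitudes. It also puts the instrument described as validated ahead of the one still to be developed in Phase 1. If the sponsor regards attitude as the main target, the order can be reversed, provided that it is fixed before the data are analysed.

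The cost is two sentences of text and no extra patients. The price is that ATT cannot be claimed if KAST fails, and that power to claim ATT is below 80%. If both scores must keep equal rank, the alternatives in step 4 need more patients: 41 or 44 instead of 34, or 241 or 260 instead of 199.

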These days are subject to change given the course of the patient's hospitalization and any patient-specific barriers that prevent the collection of data. If a patient is unavailable or experiences an exacerbation or decompensation of their condition, the assessment or

intervention will be postponed until the patient is able to participate. If a patient experiences suicidal ideation or thoughts of self-harm, this will be fully investigated by the healthcare provider to determine if intent and plan are present. Every effort will be made to protect patients from self-harm while on the unit. Depending on the severity (passive versus active), the educational resources or assessments may be postponed until the patient is able to resume participation.

Of note, patients will be selected to carry out the KAST and ATT randomly by either of the resident physicians using a randomization tool. There will be 4 resident physicians carrying out the patient questionnaires and educational sessions. They will be assigned a number 1-4, which an excel- integrated tool will use to randomize which physician will administer the KAST and ATT questionnaires. The resident that will complete the next task will be the one assigned the next chronological number, and so on. For example, resident #2 is randomly selected to do the KAST and ATT questionnaires. Then, the resident assigned #3 will carry out the first educational session. This is to ensure the patient does not interact with a resident physician more than once while on the inpatient unit. Follow up calls will be carried out by either resident physician. Patient identities will be concealed from the individuals analyzing the data by using numerical identifiers.

Patients will act as their own control, as their initial KAST and ATT questionnaires will serve as a baseline for which to compare future KAST and ATT questionnaires. At the end of each phase, the clinician will transfer the patient's answers electronically into the dataset. Patients will be paid \$50 through Clincards issued by the research team upon discharge from the hospital. Assessments and questionnaires will be carried out on paper, while the educational resources will be provided electronically via tablet.

Procedures	Day 1	Day 2	Day 3	Day 4	Months 1 -12
KAST	X			X	
ATT (ANT + DAI)	X			X	
Video		X			
Psychoeducational Meeting 1		X			
Educational Brochure			X		
Psychoeducational meeting 2			X		
Monthly follow up phone calls with MARS					X

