Phase 3: Data Extraction

This project will require approval from both the Louisiana Health Sciences Center-New Orleans Institutional Review Board and the University Medical Center- New Orleans Office of Research. A formal data request will be made to UMCNO with the needed information for data abstraction. Data metrics will be pulled from the UMCNO electronic medical record

(EMR). Information that will be extracted from the electronic health record includes race, gender, ethnicity, age, mental health diagnosis, number of hospital admissions and Emergency room presentations, pharmaceutical agents prescribed, type of insurance, if any, housing status, and highest level of education achieved. This will occur once patients have been stabilized and consented to participate in the study.

For further clarification on the proposed timeline:

- a. a. Recruitment: This will be an ongoing task from the start of the study, where prospective patients will be identified from the Behavioral Health Emergency Room (BHER) and BH inpatient units. Consent will be obtained when patients are stable.
- b. Administration of questionnaires, completion of educational interventions: Please see the proposed timeline table in the protocol. An exact timeline cannot be given, as events are contingent upon the patient's ability to participate and thus will be different between individuals.
- c. Data collection will be ongoing and will last until the final follow-up data from the last patient is obtained.

Follow up

Patients will receive monthly follow-up calls that last approximately 5-10 minutes each. During these calls, they will be asked questions about medications, symptom control, and follow-up. A sample of questions is listed below. In addition, they will also be asked to provide answers to the questions listed on a modified version of the Medication Adherence Rating Scale (MARS).

1. Are you taking any medications to manage your symptoms: yes/ no?
2. How has that medication affected your symptoms: better/ worse/ no change?
3. If you are no longer taking your medications, what is the reason: ASE/ unable to pay for prescription/ unable to pick up prescription?
4. If applicable, have you been going to the scheduled follow up visits with your behavioral health provider: yes/ no?
5. If you answered no to the previous question, what is the reason: transportation/ time conflict/ forgot?
6. Have you been admitted to a psychiatric facility since your last follow up call: yes/ no?

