7. If so how many times: 1-3/ 3+?

Table 1: 10-item medication adherence rating scale (MARS)		
No.	Questionnaire	Question Answer
1.	Do you ever forget to take your medication?	Yes/No
2.	Are you careless at times about taking your medication?	Yes/No
3.	When you feel better, do you sometimes stop taking your medication?	Yes/No
4.	Sometimes if you feel worse when you take the medication, do you stop taking it?	Yes/No
5.	I take my medication only when I am sick	Yes/No
6.	It is unnatural for my mind and body to be controlled by medication	Yes/No
7.	My thoughts are clearer on medication	Yes/No
8.	By staying on medication, I can prevent getting sick.	Yes/No
9.	I feel weird, like a “zombie” on medication	Yes/No
10.	Medication makes me feel tired and sluggish	Yes/No

Adverse Events

This study does not anticipate adverse events beyond psychological discomfort as it relates to the awareness and processing of a newly diagnosed or established diagnosis of a mental health condition. However, all adverse events will be collected and reported in accordance with the safety event and quality reporting as outlined by Janssen. This will include adverse events (AE), serious adverse events (SAE) including lack of effect of pharmacological intervention, reports of drug exposure during pregnancy, and abnormal pregnancy outcomes. Definitions of adverse events and contact information are listed below:

Adverse Event (AE)

Any untoward medical event in a patient administered a pharmaceutical product which does not necessarily have to have a causal relationship with the treatment. An adverse event can be any unfavourable and unintended sign (including abnormal finding or lack of expected pharmacological action), symptom, or disease temporarily associated with the use of a medicinal (investigational or non-investigational) product, whether or not related to that (investigational or non-investigational) product.

This includes any occurrence that is new in onset or aggravated in severity from the baseline condition, or abnormal results of any diagnostic procedures, including laboratory test abnormalities.

Adverse Event of Special interest

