Adverse events of special interest are events that the Company is actively monitoring as a result of a previously identified signal (even if non-serious). There are no required Adverse events of special interest of paliperidone to be reported to the Company. In case of any amendments to the AESI list, Company will notify the Investigator. Investigator will ensure that these changes are updated in the protocol as soon as practical.

Serious Adverse Event (SAE)

Any adverse event occurring that:

- Results in death
- Is life-threatening
- Requires in-patient hospitalization or prolongation of existing hospitalization
- Results in persistent or significant disability/incapacity
- Is a congenital anomaly/birth defect
- Any suspected transmission of any infectious agent via administration of a medicinal product
- Is considered medically significant*

*Any untoward medical occurrence that is considered medically significant. Medical and scientific judgment should be exercised in deciding whether expedited reporting is appropriate in other situations, such as important medical events that may not result in death, be life-threatening or require hospitalization but may be considered a serious adverse drug experience when, based on appropriate medical judgement, that may jeopardize the patient or subject and may require medical or surgical intervention to prevent one of the other outcomes listed in the bulleted list above. Examples of such medical events include allergic bronchospasm requiring intensive treatment in an emergency room or at home, blood dyscrasias or convulsions that do not result in hospitalization, or development of drug dependency or drug abuse or malignancy.

Hospitalization

For reports of hospitalization, it is the sign, symptom or diagnosis which led to hospitalization that is the serious event for which details must be provided. Any event requiring hospitalization or prolongation of hospitalization that occurs during a study must be reported as a serious adverse event, except hospitalizations for the following:

- Hospitalizations not intended to treat an acute illness or adverse event (e.g., social reasons such as pending placement in long-term care facility)

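### The only listed monthly-call question on admissions covers psychiatric facilities, while the serious adverse event rule covers hospitalization generally, so medical admissions after discharge may be missed

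*Protocol*

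**What the plan says.** The schedule table at the end of Phase 2 shows one activity after Day 4, in the column for Months 1 to 12: "Monthly follow up phone calls with MARS". The Follow up section gives the content of these calls. Patients are contacted monthly for about 5 to 10 minutes, and "they will be asked questions about medications, symptom control, and follow-up". Seven questions are then set out, introduced by the words "A sample of questions is listed below". Question 6 is "Have you been admitted to a psychiatric facility since your last follow up call", and question 7 asks for the number of such admissions in two bands. The modified MARS is also administered.

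The Adverse Events section makes a broad commitment: "However, all adverse events will be collected and reported in accordance with the safety event and quality reporting as outlined by Janssen". In-patient hospitalization is one of the criteria for a serious adverse event. The Hospitalization paragraph adds: "Any event requiring hospitalization or prolongation of hospitalization that occurs during a study must be reported as a serious adverse event". Two exceptions follow: stays that do not treat an acute illness or adverse event, and surgery or procedures planned before entry. The same paragraph requires a report to detail the clinical cause of the admission. Serious adverse events are reportable within 15 calendar days of awareness.

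**The concern.** The question and the reporting rule differ in scope. The rule takes in any event needing hospitalization, whatever the type of hospital. The question takes in psychiatric facilities only. A patient admitted to a general hospital for an acute medical problem, including one related to medication, can answer question 6 with a correct no. The caller then has no listed prompt that would bring the event to light.

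What is at stake is the completeness of the safety data for up to 12 months per patient. The possible loss is also selective: psychiatric admissions are asked about at every call and other admissions are not. A summary of serious adverse events built from these calls could therefore lean toward psychiatric relapse. The reporting clock starts at awareness, so for an event nobody asks about it may never start.

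**Working it through.** The protocol gives no figure on this point to reproduce, and no arithmetic decides it. The check compares the relevant texts.

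1. **Scope of the rule** (Serious Adverse Event and Hospitalization paragraphs). It covers events requiring hospitalization or prolonging it, with no limit by type of facility. An unplanned acute medical admission is intended to treat an acute illness, so the first exception does not apply. It was not planned before entry, so the second does not apply either. It is reportable.

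2. **Scope of the listed questions** (Follow up, questions 1 to 7).
   - Questions 1 to 3 concern medication use, its effect on symptoms and reasons for stopping.
   - Questions 4 and 5 concern visits to the behavioral health provider.
   - Questions 6 and 7 concern psychiatric admissions and their number.
   - The nearest item to a general safety question is ASE, offered as a reason for stopping medication in question 3. It identifies neither an admission nor its seriousness.

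3. **MARS items** (Table 1). All ten concern medication-taking and beliefs about or experience of medication. None asks about admission.

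4. **Other scheduled contacts** (schedule table). There are none after the inpatient phase apart from the monthly calls.

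5. **Medical record** (Phase 3: Data Extraction). The extraction includes the number of hospital admissions and emergency presentations, not limited to psychiatric ones. It is drawn from the study hospital's record only, it is a count, and it is placed at the point where patients are stabilized and have consented. No repeat extraction in Months 1 to 12 is stated, and an admission to another hospital is not described as captured.

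6. **Detail collected against detail required.** For a psychiatric admission, questions 6 and 7 yield a yes or no and a banded count. The Hospitalization paragraph requires the underlying clinical cause. So the listed questions fall short of the rule on content as well as scope.

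Steps 2 to 5 leave no stated question or procedure that would elicit a non-psychiatric admission after discharge. Step 1 shows that such an admission is reportable.

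**The case against.** The strongest case against the point is that it treats an illustrative question as the safety instrument. The list is expressly a sample, so the full call script may ask more. Nothing in the protocol says that question 6 exists to serve the serious adverse event rule. It follows questions on medication and behavioral health visits, and reads naturally as a psychiatric readmission item. The protocol separately commits to collecting all adverse events and refers to a case report form, a serious adverse event form and the funder's procedures, any of which could hold the elicitation wording. Resident physicians make the calls and can ask beyond a script. The adverse event definition is framed around patients given a pharmaceutical product, which may narrow the rule somewhat. Hospitalization is not an endpoint, no comparison of serious adverse events is planned, and the intervention is educational.

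Much of this stands. A reader might infer that the call asks about psychiatric admission and nothing else, and that medical admissions will be missed unless volunteered. The documents do not support that: a sample list cannot show what the full script omits, and the general commitment to collect adverse events is explicit. A reader might also apply an assumed yearly admission rate to the planned sample and present the result as events lost. That is not supported either. The protocol gives no rate, and such a count would also assume no fuller script, no volunteering and no other source.

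What does not fall away is the mismatch itself. The protocol chose to write one admission question and limited it to psychiatric facilities. Its statement of what the calls cover names neither adverse events nor general hospitalization. If question 6 is purely a readmission item, then no listed question serves the hospitalization rule at all. The timeline's remark that data collection continues until the last follow-up does not say that the record extraction is repeated.

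**Conclusion.** The point holds in a limited form. The only listed call question on admissions is narrower than the protocol's own rule on hospitalization, and no other listed question or stated repeat extraction fills the gap in Months 1 to 12. Non-psychiatric serious adverse events may therefore be missed, and the safety data may tilt toward psychiatric admissions.

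The size is not known and cannot be derived from the documents. The conclusion assumes that the unseen remainder of the script and the forms contain no broader admission question; if they do, the gap closes in practice and only the protocol wording needs aligning. The paired comparisons of KAST and ATT are untouched, since both scores are collected before the follow-up calls begin. This is a minor, inexpensive improvement, not a flaw in the main analysis.

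**What to change.** Reword question 6 to ask about admission to any hospital, psychiatric or medical. For each admission, record the type of facility and the reason, so that the entry supplies what the Hospitalization paragraph requires and psychiatric admissions can still be reported separately. If the full call script or case report form already asks this, bring the protocol's sample question into line with it.

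The cost is seconds per call and possibly a few more serious adverse event forms. The change addresses hospitalization only; it does not prompt for the other kinds of serious event that the safety section lists.
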